7.3.2. Transthyretin

On scheduled visits, serum samples will be collected within one hour prior to dosing and analyzed for total TTR levels using an enzyme linked immunosorbent assay (ELISA) method at a central laboratory.

7.3.3. Modified Body Mass Index

Assessment of nutritional status, which has been linked to autonomic dysfunction will be measured by the mBMI. Since the mBMI takes into account the serum albumin values along with BMI (function of height and weight), it corrects for hypoalbuminemia and is considered more reflective of nutritional status than BMI alone. This calculation will be performed by the Sponsor on the reported data (ie, whenever body weight is recorded, except end of study) and not performed at the site.

7.3.4. Estimated Glomerular Filtration Rate

Estimated glomerular filtration rate will be calculated using the MDRD formula by the central laboratory. If this parameter met eligibility criteria at Screening/Baseline, then dosing can proceed prior to receiving pre-dose Day 0 results.

7.3.5. Fat Pad Biopsy

Fine-needle aspirates of the abdominal fat pad (FNAFP) for amyloid quantification will be collected only at certain sites and in only patients who have provided additional voluntary consent. Subsequent scheduled biopsies may not be collected depending on the status of the Screening/Baseline biopsy sample. Repeat Screening/Biopsy samples may be collected if the initial sample is not of sufficient quality. The voluntary fat pad biopsy should only be obtained once during Screening.

Details on FNAFP collection, processing, and shipment will be in the Site Operations Manual.

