- t The 6-MWT will be conducted twice during the Screening/Baseline visit (practice and actual test to be performed at least 1 hour apart) and both tests must be completed within 28 days of Day 0. The assessments will include pre- and post-walk assessment of O₂ saturation, blood pressure, heart rate, and the Borg scale ratings for fatigue and dyspnea. The higher of the 2 values at Screening/Baseline will be used for eligibility purposes. The 6-MWT will be conducted only once, prior to dosing, at all subsequent time points.
- u An ECHO done at Screening/Baseline and for all subsequent time points will be evaluated by a central laboratory.
- v Cardiac MRI with late gadolinium enhancement (LGE) is only to be obtained in patients without contraindications (i.e., pacemakers, defibrillators, inadequate renal function or allergy to gadolinium) at selected sites on a subset of patients (up to 60). All time points will be evaluated by a central lab.
- w ^{99m}Tc scintigraphy by 3D SPECT during the study is an exploratory assessment and is not intended for diagnostic purposes or to fulfill eligibility criteria for the study. Either ^{99m}Tc pyrophosphate (^{99m}Tc-PYP) or ^{99m}Tc-3,3-diphosphono-1,2-propanodicarboxylic acid (^{99m}Tc-DPD) can be used as a tracer. The tracer should not be changed for the patient during the study. This assessment will only be performed at selected sites on a subset of patients (up to 60). All time points will be evaluated by a central lab.
- x This assessment is voluntary and will only be performed at selected sites. Additional time points may not be collected depending on the status of the Screening/Baseline biopsy sample. Repeat Screening/Baseline biopsy samples may be collected if the initial sample is not of sufficient quality.
- y Patients enrolling in the open-label extension study (ALN-TTRSC-006) will not need to complete the Month 19 visit. For these patients, Month 18 assessments will constitute the End of Study assessments.
- z Serum chemistry (including LFTs) and coagulation tests are to be performed at Week 17 and Week 21.

aa Serum SPEP with IFE, urine SPEP with IFE and serum FLC is to be performed at Screening/Baseline. If available, documented local results obtained within 1 year of Screening/Baseline may be used to fulfill this requirement.

bb These assessment will only be performed for patients enrolling in the ALN-TTRSC-006 study.

TABLE OF CONTENTS

STUDY	SYNOPSIS	3
TABLE (OF CONTENTS	15
LIST OF	TABLES	20

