3.3. Efficacy Endpoints

3.3.1. Primary endpoints:

The co-primary endpoints of the study are to evaluate the difference between the ALN-TTRSC and placebo groups for:

- 1. Change in 6-MWD at 18 months compared to baseline
- 2. Percent reduction in serum TTR burden over 18 months

3.3.2. Secondary endpoints:

The secondary endpoints of the study are to determine the effect of ALN-TTRSC on various clinical parameters by assessing the difference between the ALN-TTRSC and placebo groups at 18 months for:

- Composite CV mortality and CV hospitalization
- Change in New York Heart Association (NYHA) class (Appendix 1) compared to baseline
- Change in Kansas City Cardiomyopathy Questionnaire (KCCQ) compared to baseline
- Cardiovascular (CV) mortality
- CV hospitalization

Confidential

All-cause mortality

3.3.3. Exploratory endpoints:

The exploratory endpoints of the study are to determine the difference between the ALN-TTRSC and placebo groups in the change from baseline at 18 months in the following measurements:

- EuroQOL (EQ-5D) questionnaire
- Echocardiogram parameters
- Karnofsky Performance Status (Appendix 2)
- Troponin T and I, and N-terminal prohormone of B-type natriuretic peptide (NT proBNP) levels
- Cardiac magnetic resonance imaging (CMR) parameters (only at selected sites)
- 99m Technetium scintigraphy parameters (only at selected sites)
- Amyloid in abdominal wall fat pad aspirates
- Polyneuropathy Disability (PND) Score (Appendix 3)
- Modified body mass index (mBMI)
- Estimated glomerular filtration rate (eGFR)
- HF hospitalization

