7 STATISTICAL METHODS

7.1 General Principles

All data processing, summarization and analyses will be performed using the SAS Version 9.3 (or later) of the SAS® statistical software package.

All data collected will be sorted and presented in listings by treatment group, site, patient identification, assessment, relative day (see Section 6.1 for definition) and visit (where applicable), unless otherwise specified.

Data will be presented in summary tables by treatment group (revusiran, placebo), assessment and visit (where applicable).

Descriptive summary statistics for continuous variables will include the number of patients/observations (N), mean, standard deviation (SD), median and range (minimum, maximum).

Descriptive summary statistics for categorical variables will include frequency counts and percentages for each category [n (%)]. A category of missing will be included if the number missing is greater than zero. Unless stated otherwise in the table shells, the denominator for percentage calculations will be the number of patients in the analysis population.

All statistical tests will be 2-sided and performed at the 5% significance level, unless otherwise specified. Confidence intervals of 95% will be provided where appropriate.

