7.6.3.6 Amyloid in Abdominal Wall Fat Pad Aspirates

Tabulations of result of test and grade of test will be generated for each treatment group by visit.

Note: This procedure is voluntary for the patients. A summary of sites where patients volunteered for this procedure will be tabulated.

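### SAP 7.6.3.6 tabulates fat pad amyloid by visit without pairing patients, so it cannot show the change from baseline that the protocol sets as the endpoint

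*Protocol*

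**What the plan says.** Protocol 3.3.3 introduces the exploratory list, which includes fat pad amyloid, as the difference between arms "in the change from baseline at 18 months in the following measurements". Protocol 7.3.5 says that the aspirates are taken to quantify amyloid, at certain sites and with separate voluntary consent. The schedule of assessments (Table 1-1) places them at Screening/Baseline, Month 12, Month 18 and early termination.

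Later sampling is conditional. Protocol 7.3.5 states that "Subsequent scheduled biopsies may not be collected depending on the status of the Screening/Baseline biopsy sample", and footnote x of Table 1-1 says the same: "Additional time points may not be collected depending on the status of the Screening/Baseline biopsy sample". Neither place defines status.

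On the Screening sample, 7.3.5 says both "Repeat Screening/Biopsy samples may be collected if the initial sample is not of sufficient quality" and "The voluntary fat pad biopsy should only be obtained once during Screening". Footnote x repeats the permission and footnote b repeats the restriction.

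The whole analysis in SAP 7.6.3.6 is "Tabulations of result of test and grade of test will be generated for each treatment group by visit", plus a tabulation of the sites where patients volunteered. Two general rules in SAP 7.1 also apply: "Unless stated otherwise in the table shells, the denominator for percentage calculations will be the number of patients in the analysis population", and "A category of missing will be included if the number missing is greater than zero". SAP 7.6 places all efficacy analyses on the mITT population.

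**The concern.** A by-visit count shows change only if the same patients stand in each column. Here the protocol allows the later columns to lose patients for a reason tied to their own Screening sample, and the SAP has no rule for that. A reader who compares the Screening column with the Month 18 column may be comparing two different groups.

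The omission also looks unintended. In SAP 7.6.3 the other measured items on the protocol's list all receive a change or shift display: echocardiography, Karnofsky status, troponins and NT-proBNP, CMR, scintigraphy, PND, mBMI, eGFR and EQ-5D. Heart failure hospitalization is an event count, so baseline change does not apply to it. Fat pad amyloid is the only measured item without one.

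At stake is whether a voluntary needle procedure yields the summary it was meant to give. No test, and no primary or secondary conclusion, depends on it.

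**Working it through.** **Inputs.** Neither document gives a number of volunteers, a positivity rate or a skipping rate for this endpoint, so there is no plan figure to reproduce. Assumed: Screening positivity p from 0.3 to 0.9, and the share of Screening-negative patients not re-sampled, s(neg), from 0 to 1. The share of positives not re-sampled is s(pos), set to 0 unless stated. Throughout, no patient's amyloid status changes, so any movement is an artefact.

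**1. Denominator = patients tested at the visit, negatives skipped.**

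Apparent positivity = p(1 − s(pos)) / [p(1 − s(pos)) + (1 − p)(1 − s(neg))].

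For p = 0.5 and s(neg) = 0.5: 0.5 / (0.5 + 0.5 × 0.5) = 0.5 / 0.75 = 67%.

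| Screening positivity | 25% of negatives skipped | 50% | 75% | 100% |
|---|---|---|---|---|
| 30% | 36% | 46% | 63% | 100% |
| 50% | 57% | 67% | 80% | 100% |
| 70% | 76% | 82% | 90% | 100% |
| 90% | 92% | 95% | 97% | 100% |

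**2. Denominator = mITT population with a missing row (SAP 7.1 default).** Take 200 patients in all, and assume 60 are sampled, of whom 30 are positive. Screening reads 30/200 = 15% positive, 15% negative, 70% missing. If every negative is skipped later, the table reads 15% positive, 0% negative, 85% missing. The positive percentage does not move, but the negatives vanish although nobody changed.

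That flat line is not a measure of change either, because the missing row mixes non-volunteers, patients skipped by rule, dropouts and deaths. The sample-size section assumes that 20% of placebo and 13% of active patients die before 18 months. If the 15% applies in each arm, deaths are unrelated to amyloid status and all surviving positives are re-sampled, it becomes 15 × 0.80 = 12.0% on placebo and 15 × 0.87 = 13.05% on active drug, with no change in amyloid.

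**3. Status means sample adequacy, unrelated to positivity.** With s(pos) = s(neg) the formula returns p, so among evaluable samples 30%, 50% and 70% stay at 30%, 50% and 70%.

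**4. Positives skipped instead.** With s(pos) = 0.5 and s(neg) = 0, 50% becomes 0.25 / 0.75 = 33%, 30% becomes 0.15 / 0.85 = 18%, and 70% becomes 0.35 / 0.65 = 54%. Even the direction depends on the undefined word.

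**5. Between arms.** With the same p and the same skipping rule in both arms, the formula gives the same value in each, so the artefactual difference is 0.

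**6. Paired display.** Restricted to patients with an evaluable sample at both visits, positivity is identical at the two visits when nobody changes. The apparent change is 0 for every p and every skipping share.

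**The case against.** The strongest reply is that the SAP already guards against the artefact. Its default denominator is the mITT population with a missing row, so skipped negatives cannot inflate the positive percentage. The table shells, which could override that default, are not in the documents. This stands: a reader might infer that positivity will appear to rise on study, and the documents do not support that. A rise needs both negative-triggered skipping and a non-default denominator.

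Second, the protocol says status, not result, and the adjacent sentence concerns sample quality. Adequacy is at least as natural a reading. The wording is also permissive, so skipping every negative (the 100% column above) is an extreme and not an expectation. This stands too.

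Third, a reader might infer that clearance of amyloid on active drug would look like worsening. Suppose 60% are positive at Screening, all negatives are skipped, percentages use patients tested, and 20% of active-arm positives clear while no placebo patient does. The active arm goes from 60% to 80%. But the placebo column beside it reads 100%, so the Month 18 contrast favours active drug by 20 points. SAP 3.3 words the aim as a difference between arms at 18 months, and the planned table does show that contrast for whoever was sampled.

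Finally, the endpoint is exploratory with no test planned, and the listings under SAP 7.1 would let someone rebuild the pairs. That limits the harm. But pairs rebuilt afterwards from listings are not a pre-specified summary, and nothing in this reply supplies the change from baseline that protocol 3.3.3 names.

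**Conclusion.** The point holds as a mismatch between endpoint and analysis. The planned table cannot report within-patient change, and conditional re-sampling means that its columns may not describe the same patients. This rests on the text alone and needs no assumption about rates.

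The size of any distortion cannot be fixed from the documents. It ranges from none (skipping unrelated to positivity, or the positive percentage on the default denominator with no deaths) through 50% reading as 67% (half the negatives skipped, patients tested as denominator) to 100% in the extreme case. It would run downward if positives were the ones skipped. The skipping rule alone does not bias the comparison between arms, provided that Screening positivity and the way the rule is applied are alike in both.

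The conflict over repeat Screening samples is a wording matter. It affects only patients whose first sample is inadequate, but a site that follows the once-only sentence would leave such a patient without a usable baseline. Overall this is a minor, inexpensive improvement.

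**What to change.** In SAP 7.6.3.6:

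- Keep the by-visit counts and state their denominator.
- Add a shift table of result and grade from Screening to Month 12 and to Month 18, by arm, in patients with an evaluable sample at both visits, with that number as the denominator. PND in SAP 7.6.3.7 already has both a shift display and by-visit counts.
- Count non-collection by reason at each visit: skipped because of the Screening sample, inadequate, declined, withdrawn, died.
- Where a quantified amyloid value exists, summarise its paired change by arm.

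In the protocol, define status in 7.3.5 and footnote x. Reconcile the permission to repeat a poor Screening sample (7.3.5, footnote x) with the once-only statement (7.3.5, footnote b).

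The cost is one table shell and a few sentences, with no extra samples. The paired table will hold fewer patients than the by-visit counts. Protocol 9.2 has the SAP finalized before database lock, and SAP 7.8 already foresees an update for the futility criteria, so the change can go in then.

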7.3.6. Karnofsky Performance Status

Each patient's Karnofsky Performance Status (Appendix 2) will be assessed.

7.3.7. Polyneuropathy Disability Score

Ambulation will be evaluated through the PND score (Appendix 3).

7.3.8. NYHA Classification

New York Heart Association classification will be recorded. The NYHA classification scale is provided in Appendix 1.

7.3.9. Imaging

7.3.9.1. Echocardiography

An echocardiogram with Doppler will be used for assessment of cardiac structure and function. Echoes obtained at the Screening/Baseline visit will be used to assess eligibility criteria.

Details for image acquisition and upload for central review can be found in the ALN-TTRSC Site Operations Manual.

7.3.9.2. Cardiac Magnetic Resonance Imaging

Cardiac magnetic resonance imaging with late gadolinium enhancement will only be performed on patients without contraindications (ie, pacemakers, severe renal failure with eGFR <30 mL/min/1.73 m², defibrillators, or allergy to gadolinium). This test will be performed only at select sites and in a subset of patients (up to 60). Patients are not required to repeat CMR if the assessment is performed within 6 months of randomization.

Details for image acquisition and upload for central review can be found in the ALN-TTRSC Site Operations Manual.

7.3.9.3. Technetium Imaging

Technetium imaging assessments performed as part of the study are for research and are not intended to be used for diagnostic purposes.

^{99m}Tc imaging by 3D SPECT during the study will be performed only at selected sites and in a subset of patients (up to 60). Either PYP-Tc or DPD-Tc can be used as the tracer. The tracer used for a patient should not be changed during the study. This test will be performed only at select sites. All time points will be evaluated by a central lab. Patients are not required to repeat ^{99m}Tc scintigraphy if assessment was performed within 6 months of randomization.

Technetium scintigraphy used to fulfill the inclusion criterion for evidence of cardiac amyloid deposition are not performed as part of the study assessments, but will be evaluated by a central reader for confirmation of the required cardiac uptake. 26, 27, 28

Details for the image acquisition and upload for central review can be found in the ALN-TTRSC Site Operations Manual.

7.3.10. **Questionnaires**

7.3.10.1. Kansas City Cardiomyopathy Questionnaire

The KCCQ is a self-administered, 23-item questionnaire that assesses physical function, symptoms, social function, self-efficacy and knowledge, and QoL. Each patient is to complete this questionnaire.

7.3.10.2. EQ-5D Quality of Life

Quality of life will be assessed through the use of the EQ-5D, a standardized 5 question instrument for use as a measure of health outcomes. Each patient is to complete this questionnaire.

7.3.11. NT-proBNP, BNP, Troponin T, and Troponin I

Blood samples will be collected and analyzed for the quantification of troponin T, troponin I, and NT-proBNP (biomarkers of cardiac status). BNP will only be collected at Screening/Baseline. Quantification of these biomarkers will be performed at a central laboratory.

7.3.12. Mortality and Hospitalization

All events will be recorded from Day 0 and beyond; reasons for mortality and hospitalization will be adjudicated by an independent Clinical Adjudication Committee.

7.4. Pharmacokinetic Assessment

Blood samples will be taken for the assessment of plasma levels of ALN-TTRSC at the following time points during the study:

- Days 0, Month 6 and Month 12: within 1 hour predose and 2.5±1 hour postdose
- A sample will be collected at the Early Termination visit, if applicable.

Exploratory analyses may also be conducted on plasma samples to evaluate metabolites of ALN-TTRSC.

7.5. Safety Assessments

7.5.1. Physical Examination

Routine physical examinations will be performed. Physical examinations will include the examination of the following: general appearance, head, eyes, ears, nose and throat, chest/respiratory, heart/cardiovascular, gastrointestinal/liver, musculoskeletal/extremities, dermatological/skin, thyroid/neck, lymph nodes, and neurological/psychiatric.

7.5.2. Vital Signs

Vital sign measurements include blood pressure, pulse rate, oral body temperature, and respiratory rate. Vital signs will be measured manually in the supine position after the patient has rested comfortably for 10 minutes. Each patient's blood pressure should be taken using the same arm. Oral temperature will be obtained in degrees Celsius, heart rate will be counted for a full minute and recorded in beats per minute (bpm), and respirations will be counted for a full minute and recorded in breaths per minute.

When vital signs are scheduled at the same time as blood draws, the blood draws will be obtained at the scheduled time point, and the vitals will be obtained prior to the blood draw. On dosing days, vital signs should be obtained prior to dosing.

For the safety of the patient, additional vital sign assessments may be added at the discretion of the Investigator.

7.5.3. Weight and Height

Height will be measured only at Screening/Baseline Visit.

Body weight will be measured in kilograms (kg) at the time points specified in the schedule of assessments (SOA).

7.5.4. Electrocardiogram (ECG)

Standard computerized 12-lead ECG recordings will be obtained. Each lead shall be recorded for at least 3 beats at a speed of 25 mm/sec. Triplicate recordings will be obtained prior to

dosing. The electrophysiological parameters assessed will be rhythm, ventricular rate, PR interval, QRS duration, QT interval, ST and T waves, Bazett-corrected QT interval (QTcB) and Fredericia-corrected QT interval (QTcF).

When an ECG is scheduled at the same time as blood draws, the blood draws will be obtained at the scheduled time points and the ECG will be obtained prior to the scheduled blood draw.

The Investigator or designee is responsible for reviewing the ECGs to assess whether the results have changed since the Screening/Baseline visit and to determine the clinical significance of the results. These assessments will be recorded on the CRF. For any clinically significant changes from Screening/Baseline (e.g., ischemic ECG changes, wave/interval changes, or arrhythmia), the Investigator must contact the CRO Medical Monitor to discuss continued participation of the patient in the study.

7.5.5. Laboratory Assessments

The following clinical laboratory tests will be performed by a central laboratory, unless indicated otherwise:

	19 reducing 20
Hematology	
Hematocrit	 Neutrophils, absolute and %
• Hemoglobin	 Lymphocytes, absolute and %
Red blood cell (RBC) count	 Monocytes, absolute and %
White blood cell (WBC) count	 Eosinophils, absolute and %
Mean corpuscular volume	 Basophils, absolute and %
Mean corpuscular hemoglobin	Platelet count
Mean corpuscular hemoglobin concentration	
Serum Chemistry	
Sodium	 Potassium
Blood urea nitrogen (BUN)	 Phosphate
Creatinine	Albumin
Uric acid	• Calcium
Lactate dehydrogenase (LDH)	Carbon dioxide
Glucose	Chloride
Liver Function Tests	
AST	Alkaline phosphatase (ALP)
ALT	Bilirubin (total and direct)
Coagulation Studies	
Prothrombin time (PT)	International Normalized Ratio (INR)
Activated partial thromboplastin time (aPTT)	
Thyroid Function Test	
Thyroid stimulating hormone (TSH)	
Serology Parameters	
Hepatitis B surface antigens (HBsAg)	 Hepatitis B surface antibodies (HBsAb)
Anti-hepatitis C virus antibodies (HCV Ab)	
Urinalysis	
Visual inspection for appearance and color	Bilirubin
pH (dipstick)	Nitrite
Specific gravity	• RBCs
Ketones	Urobilinogen
Protein	Leukocytes
Glucose	Microscopy (if clinically indicated)
Pregnancy Testing (WOCBP only)	
β-human chorionic gonadotropin	
Other	
O III CI	Urine SPEP with IFE (or documented local
Vitamin A	results within last year)
Serum SPEP with IFE (or documented local results	Serum FLC (or documented local results within
within last year)	last year)

WOCBP = women of child bearing potential

Additional and repeat testing may be performed at the discretion of the Investigator.

In the event of an unexplained clinically relevant abnormal laboratory test occurring after study drug administration, the test should be repeated and followed up at the discretion of the Investigator until it has returned to the normal range or stabilized, and/or a diagnosis is made to adequately explain the abnormality.

